9.2 SKIN PRICK TESTING

Atopic status will be determined by skin prick testing to a range of 10 common aeroallergens. Positive histamine / negative diluent controls will be included.

- Mixed grass pollen
- House dust mite (Der P)

- Silver birch
- 3 trees
- Cat dander
- Dog hair
- Mugwort
- Aspergillus fumigatus
- Cladasporium herbarum
- Alternaria alternata

≥ 1 positive reaction (wheal 3 mm greater than the negative control) will be considered diagnostic of atopy.

9.3 BLOOD (INCLUDING VIRAL SEROLOGY)

Screening visit blood (in tubes with ethylenediamine tetraacetic acid (EDTA), citrate, or heparin) will be taken for full blood count, renal function, liver function tests, glucose, clotting, CRP, vitamin D and total IgE. These will be processed in the Haematology and Chemical Pathology Laboratories of St Mary's Hospital.

Blood will also be taken on study visits as per Table 1; the specific samples taken on each visit are outlined in Table 2. Serology will be performed at screening and day 42 for detection of antibodies to rhinovirus-16 (RV-16). Serum will also be used to count cell types in the circulating blood using flow cytometry, and to assess the immune response to rhinovirus *ex vivo*.

Study day	Full blood count (EDTA 4.0mL)	Clotting (Citrate 2.7mL)	Biochem + IgE (Heparin 3.5mL)	Serum
Screening	x1	x1	x2	6mL
Day -21				80mL
Day -7	x1	x1	x2	80mL
Day 3	x1	x1	x2	10mL
Day 5	x1	x1	x2	80mL
Day 10	x1	x1	x2	10mL
Day 42	x1	x1	x2	6mL
Total (mL)	24.0mL	16.2mL	42.0mL	292mL

Table 2: Overview of blood, plasma, and serum requirements (mL)

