2 STUDY OBJECTIVES

Primary objective:

- To assess the impact of OC459 on Total Lower Respiratory Tract Symptoms Score after rhinovirus infection (sum of daily scores day 0 to day 14)

Secondary objectives:

- To assess the impact of OC459 on other clinical and laboratory parameters during rhinovirus infection:
 - Health status (assessed by Asthma Control Questionnaire (ACQ) scores)
 - Lung function (assessed by spirometry)
 - Airway inflammation (assessed by exhaled nitric oxide (FeNO) levels)
 - Airway hyperresponsiveness (assessed as the provocation concentration of histamine producing a 20% fall in FEV₁, or PC₂₀)
 - Viral load (measured by quantitative Polymerase Chain Reaction (qPCR) on nasal lavage samples)
- To determine the mechanism of action of OC459, by assessing the impact of OC459 on the following during rhinovirus infection:
 - Eosinophil recruitment (measured by cell counts in sputum and bronchoalveolar lavage (BAL); eosinophil products, e.g. Eosinophil Cationic Protein (ECP), in BAL)
 - Recruitment of other immune cells (e.g. ILC2, Th2) implicated in the prostaglandin D₂ / type 2 inflammatory pathway to the airways and/or airway mucosa (measured by flow cytometry to sort and count cells in BAL, serum and nasal scrapes; and immunohistochemistry staining of bronchial biopsies)
 - Release of inflammatory mediators implicated in the prostaglandin D₂ / type 2 inflammatory pathway (e.g. the type 2 cytokines IL-4, IL-5, IL-13; measured by multiplex immunoassay on nasosorption, nasal lavage, bronchosorption and BAL, and mRNA analysis of cells in BAL and biopsies)
- To assess whether OC459 is able to restore deficient innate antiviral responses
 - Production of cytokines (e.g. interferon (IFN) α and λ) and expression of cytokine mRNA in cells from samples (blood, BAL) and infected with rhinovirus *ex vivo*
- To assess the safety of OC459
 - Adverse event reporting, physical examinations, vital signs, and clinical laboratory parameters

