3.1 STUDY OUTCOME MEASURES

Primary outcome:

- Difference in Total Lower Respiratory Tract Symptoms Score after RV infection (sum of daily scores day 0 to day 14) between OC459 and placebo groups.

Secondary outcomes:

- Difference between OC459 and placebo groups in the following (all measured as peak and change from baseline):
 - Increase in ACQ score (health status)
 - Reduction in Forced Expiratory Volume in 1 second (FEV₁) or Peak Expiratory Flow (PEF) on spirometry
 - Increase in FeNO
 - Decrease in PC₂₀
 - Virus load in nasal lavage – total (area under the curve) for days 2-5+7+10, as well as peak and difference from baseline
 - Increase in sputum eosinophilia
 - Leukocyte numbers (e.g. ILC2, Th2) in FACS-sorted BAL, serum and nasal scrapes, and in immunohistochemistry-stained biopsies
 - Cytokine levels (e.g. IL-4, IL-5, IL-13) in nasosorption, nasal lavage, bronchosorption, BAL
 - mRNA expression of same cytokines in cells in BAL and bronchial biopsies
 - In *ex vivo* studies, protein and mRNA levels of antiviral cytokines (e.g. IFN- α , IFN- λ) produced by cells from blood, BAL, and bronchial brushings in response to rhinovirus infection
- Difference in number of adverse events in OC459 and placebo groups

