6.3.2. Secondary Mechanistic Variables

1. Blood & Sputum eosinophilia
2. Leukocyte numbers (e.g. ILC2, Th2) in BAL, blood and nasal scrapes measured by flow cytometry
3. Leukocyte numbers in immunohistochemistry-stained bronchial biopsies:
 - CRTH2+ cells (cells/mm² tissue)
 - In the submucosa
 - In the epithelium
 - EG2+ activated eosinophils (cells/mm² tissue)
 - In the submucosa
 - In the epithelium
4. Soluble Mediators (nasal and bronchial):
 - Prostaglandin D₂
 - Th2 cytokines (3): IL-4, IL-5, IL-13
 - Th1 cytokines (2): IFN- γ , IL-12p70
 - Th17 cytokines (4): IL-17A, IL-17F, GM-CSF, IL-22
 - Chemokines (7): Eotaxin, Eotaxin 3, IP-10, MDC, TARC, MIP-1 α , MIP-1 β
 - Pro-inflammatory markers (4): IL-6, IL-8, IL-1 β , TNF- α
 - Cytokines that can trigger type 2 inflammation (3): IL-25/-17E, IL-33, TSLP
 - Innate antiviral interferons (2): IFN- α , IL-29/IFN- λ 1
 - Additional (6): IL-9, IL-10, IL-15, IL-18, IL-23, MIP-3 α

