6.4. Exploratory Analysis Variables

Exploratory analysis will take place across all cell counts obtained above using flow cytometry and bronchial biopsy from blood, nasal and bronchoscopic samples: A comprehensive list of which can be found below:

- Total viable cells
- Total CRTH2+ cells

- Th2 cells (defined as CD3+CD4+CRTH2+)
 - Of which are also GATA3+
- Eosinophils (defined as CD66b+CD16-)
- Neutrophils (defined as CD66b+CD16+)
- Mast cells (defined as FcERI+Lin-CRTH2-CD117+)
- Basophils (defined as FcERI+Lin-CRTH2+CD117-)
- ILC2 cells (defined as Lin-CD127+FcERI-CRTH2+)
- ILC1 cells (defined as Lin-CD127+FcERI-CRTH2-CD117-)
- ILC3 cells (defined as Lin-CD127+FcERI-CRTH2-CD117+)

Blood samples will be assessed at day -21, day -8, day 5, day 42; nasal samples at day -21, day -8, day 5 and bronchoscopic samples at day -8, day 5 (counted by flow cytometry)

Further exploratory analysis will take place on cells obtained from bronchial biopsies from day -8 and day 5 by immunohistochemistry:

- CRTH2+ cells (cells/mm² tissue)
 - In the submucosa
 - In the epithelium
- EG2+ activated eosinophils (cells/mm² tissue)
 - In the submucosa
 - In the epithelium

Values for ACQ-6 (D-9, D10) will also be analysed.

In addition, exploratory analysis will take place to investigate antiviral response. This will consist of the following variables:

- Protein levels of IFN- β , - λ 1 and - λ 2/3 in supernatants of cells taken from subjects and infected with virus *ex vivo*.
- mRNA levels of IFN- β , - λ 1 and - λ 2/3 a panel of interferon stimulated genes (Mx1, RIG-I, OAS, viperin, IP-10, PKC) in cell lysates from the same *ex vivo* experiments.

7. Statistical Methodology

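### The protocol names serum, a cell-free fraction, as the specimen for circulating-cell counts, and Table 2 lists no anticoagulated tube on Day -21 and no flow-cytometry tube on Day 42

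*Protocol*

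**What the plan says.** Three protocol sections name serum for counting circulating cells:

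- Section 2, in the mechanism objective: "measured by flow cytometry to sort and count cells in BAL, serum and nasal scrapes".
- Section 3.1, in the secondary outcomes: "Leukocyte numbers (e.g. ILC2, Th2) in FACS-sorted BAL, serum and nasal scrapes".
- Section 9.3: "Serum will also be used to count cell types in the circulating blood using flow cytometry". That section gives the ex vivo rhinovirus work the same source.

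For the ex vivo work the protocol disagrees with itself. Section 9.3 says serum, section 2 names blood and BAL as the sources, and section 3.1 refers to antiviral cytokines "produced by cells from blood, BAL, and bronchial brushings in response to rhinovirus infection".

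The SAP says blood. Section 6.3.2 lists "Leukocyte numbers (e.g. ILC2, Th2) in BAL, blood and nasal scrapes measured by flow cytometry", and section 6.4 sets the days: "Blood samples will be assessed at day -21, day -8, day 5, day 42". SAP 7.4.1 specifies a between-group comparison of the change in blood flow-cytometry counts from Day -21 to Day -8.

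Section 9.3 refers to Table 2 for the samples taken at each visit. Table 2 has four columns: EDTA for full blood count, citrate for clotting, heparin for biochemistry and IgE, and Serum. No column is for anticoagulated research blood.

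**The concern.** Serum is the fluid left after blood has clotted. It has no leukocytes to sort or count, and none to infect with rhinovirus. The error appears in the objective, the outcome, the procedure and the collection table, so it is more than a single slip. Table 2 is what site staff would follow when choosing tubes, and the SAP specifies no tube, so its use of the word blood does not correct the collection instruction.

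At stake is the blood part of the leukocyte recruitment endpoint, a secondary mechanistic variable in SAP 6.3.2, and in particular the pre-inoculation drug effect on circulating cells tested in SAP 7.4.1. Day 42 raises a smaller, separate question: the SAP lists a flow-cytometry sample for which the protocol assigns no tube.

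**Working it through.** **Inputs.** Protocol Table 2, set beside the blood flow-cytometry days in SAP 6.4:

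| Table 2 day | EDTA (4.0 mL) | Citrate (2.7 mL) | Heparin (3.5 mL) | Serum column | Flow day in SAP 6.4 |
|---|---|---|---|---|---|
| Screening | 1 | 1 | 2 | 6 mL | no |
| -21 | none | none | none | 80 mL | yes |
| -7 | 1 | 1 | 2 | 80 mL | yes, as Day -8 |
| 3 | 1 | 1 | 2 | 10 mL | no |
| 5 | 1 | 1 | 2 | 80 mL | yes |
| 10 | 1 | 1 | 2 | 10 mL | no |
| 42 | 1 | 1 | 2 | 6 mL | yes |

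**Step 1: reproduce the stated totals.**

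- EDTA: 6 × 4.0 = 24.0 mL. Stated 24.0 mL.
- Citrate: 6 × 2.7 = 16.2 mL. Stated 16.2 mL.
- Heparin: 6 × 2 × 3.5 = 42.0 mL. Stated 42.0 mL.
- Serum: 6 + 80 + 80 + 10 + 80 + 10 + 6 = 272 mL. Stated 292 mL, a difference of 20 mL (20/292 = 6.8%).

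The first three totals come out only with six tube-bearing rows. The blank Day -21 cells are therefore part of the table as intended and not an artefact of text extraction.

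The Serum total does not reproduce. The gap would close if Day 42 were 26 mL (6 + 20), or if Days 3 and 10 were 20 mL each (10 + 10 extra). The documents do not say which entry is wrong, or whether the total is.

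**Step 2: the three large draws.** 3 × 80 = 240 mL of the 272 mL falls on Days -21, -7 and 5. Apart from Day -7 against Day -8, these are three of the four SAP flow days. That pattern fits research blood for cell work recorded under a wrong header.

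**Step 3: which specified test is exposed.** SAP 7.4.1 needs cells on Day -21 and Day -8. On Day -21 the only entry is 80 mL of serum. Read literally, there are no cells at that end of the comparison, and no other tube was drawn that day to substitute. Days -7 and 5 do have EDTA and heparin tubes, but these are assigned to other tests.

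**Step 4: Day 42.** All tubes that day hold 4.0 + 2.7 + 7.0 + 6 = 19.7 mL. The 6 mL in the Serum column equals the screening draw, where serology but no flow cytometry is planned, and serology is also due on Day 42. None of the tubes is assigned to flow cytometry. On use of the data, SAP 7.4.1 covers Day -21 to Day -8, and the leukocyte analysis in SAP 7.3.2 (Tables 3.15 and 3.16) covers Day -8 and Day 5. No listed test uses Day 42 flow counts.

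**Step 5: visit day.** Table 2 has a Day -7 row. Table 1 of the protocol and the SAP (sections 4.9, 4.10 and 6.4) place that blood sample on Day -8.

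**The case against.** The best reply is that this is loose wording. The disputed sentence in 9.3 itself speaks of circulating blood, under a section headed Blood. The SAP, which governs the analysis, says blood everywhere. Table 2's caption mentions plasma as well as serum, yet no column is headed plasma, so Serum may simply be the header for all research blood. The 80 mL draws match the days on which cells are needed. This reply largely stands: the most likely explanation is a wrong label on a sample that was planned. It does not remove the need to correct the table, because Day -21 shows no anticoagulated tube and a specified test depends on that day.

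Three stronger readings are tempting, and the documents do not support them.

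- A reader might infer that the blood-cell endpoints cannot be measured. That follows only if the Serum header is taken literally, against the SAP and the volumes drawn.
- A reader might infer that the whole protocol takes ex vivo cells from serum. Only 9.3 does. The only between-group ex vivo analysis that the SAP details (7.4.2) uses bronchial epithelial cell cultures, and the SAP labels that objective exploratory.
- A reader might compare 6 mL with 80 mL and conclude that Day 42 counts would be much less precise. That assumes the whole draw goes to flow cytometry. The documents state no flow aliquot or minimum volume, 9.3 shares the same sample with the ex vivo work, EDTA and heparin tubes are also drawn on Day 42, and the column containing the 6 mL does not add up.

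**Conclusion.** The point holds as a specimen and collection-table error. Protocol 2, 3.1 and 9.3 name a cell-free specimen for cell counts, and 9.3 does so for the ex vivo response as well, in conflict with sections 2 and 3.1 and with the SAP. Followed literally, Table 2 leaves one specified comparison, the Day -21 to Day -8 change in blood cell counts, without Day -21 cells. Day 42 is a real but minor mismatch, because its counts enter no listed test.

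The conclusion rests on two assumptions: that Table 2 is the operative collection instruction, as 9.3 indicates, and that no laboratory manual outside these documents already specifies the correct tube. If such a manual exists, only the inconsistency between documents remains. The primary endpoint comes from symptom diaries and is not touched.

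**What to change.** 1. In Protocol 2, 3.1 and 9.3, replace serum with the anticoagulated blood specimen actually needed for flow cytometry and, in 9.3, for the ex vivo work. Name the anticoagulant that the laboratory procedure requires.
2. Split the Table 2 Serum column into serum and anticoagulated research blood, with a volume for each visit, including Day -21.
3. Either assign a flow-cytometry tube on Day 42 in Table 2, or remove Day 42 from the blood days in SAP 6.4.
4. In the same edit, correct whichever is wrong of the Serum entries and the 292 mL total, and reconcile Day -7 with Day -8. Settle the total before adding any Day 42 tube, because the present figure cannot show whether there is room for it.

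The cost is small: wording and table corrections. Changing the tube type adds no blood. Removing Day 42 loses one exploratory timepoint that no listed test uses; keeping it requires one tube to be assigned. If samples have already been taken, the record should state which tubes were used on each flow day, so that readers can see which comparisons have cells behind them.

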9.4 CLINICAL SYMPTOM SCORES (INCLUDING ACQ)

Patients will be required to keep a diary card of both upper and lower respiratory tract symptoms during the study period (see Appendices). The diary cards will be commenced 21 days prior to inoculation (on day -21) to derive a baseline symptom score. Symptom scores will be kept daily for 6 weeks post-inoculation until the convalescent visit. Spirometry measurements and drug compliance will be recorded on the same diary cards.

Upper Respiratory Tract Symptoms

The diary card of upper respiratory tract symptoms will be started 21 days prior to inoculation. A total upper respiratory clinical symptom score will be derived using a scale of 0 to 3 (absent, mild, moderate and severe) for each of the following eight respiratory symptoms: sneezing, headache, malaise, fever/chills, nasal discharge, nasal obstruction, sore throat and cough, according to previously established criteria [23]. Symptoms will be recorded at the same time of day and before any procedures such as bronchoscopy are performed. An example is shown below:

Symptom	Day 1	Day 2	Day 3	Day 4	Day 5	Day 6	Day 7
Sneezing							
Headache							
Malaise							

Fever/chills							
Nasal discharge							
Nasal obstruction							
Sore throat							
Cough							
Total score							

0 = absent, 1 = mild, 2 = moderate, 3 = severe

The maximum clinical severity score on any one day would be 24. Individual symptom scores will be accumulated over the six-day period from the onset of the cold and the recording on the day prior to inoculation subtracted. Thus, for a patient who has a score of zero on day -1 prior to inoculation, the maximum cumulative score for the six days is 144.

Lower Respiratory Tract Symptoms

A diary card of lower respiratory tract symptoms will be completed with a scoring system as outlined below:

Symptom	Day 1	Day 2	Day 3	Day 4	Day 5	Day 6	Day 7
Cough on waking							
Wheeze on waking							
Daytime cough							
Daytime wheeze							
Daytime breathlessness							
Nocturnal cough, wheeze, breathlessness							
Total score							

0 = absent, 1 = mild, 2 = moderate, 3 = severe

An exacerbation of asthma is defined as an increase in the total respiratory score of at least 2 points over baseline on 2 consecutive days.

Asthma Control Questionnaire (ACQ)

The ACQ is a standard measure of disease severity and combines symptom scores with objective parameters such as FEV₁ predicted and medication use. The ACQ should be interviewer administered. Further details are in the appendices. ACQ scoring will be assessed by study team on study visits as per Table 1.

9.5 SPIROMETRY

Spirometry will be performed using a MicroLab spirometer (CareFusion, Kent, UK) on study visits as per Table 1. At the screening visit measurements of Forced Expiratory Volume in 1 second (FEV₁) and Forced Vital Capacity (FVC) will be made:

- Posture must be consistent during a study, either standing or sitting, with no breathing limitation.
- The subject should breathe in to total lung capacity. A good tight seal by the lips round the mouthpiece is essential. The subject should then exhale forcibly into the spirometer, blowing as hard as possible and continue to residual volume.
- The best value of 3 attempts will be recorded.

The predicted or reference values for lung function measurements are those recommended by the Report Working Party for the European Community for Coal and Steel. Also incorporated are the recommendations of the British Thoracic Society (BTS) and the Association of Respiratory Technicians and Physiologists.

Reversibility: At screening, spirometry will be repeated 15 minutes after the administration of 200µg salbutamol via metered dose inhaler (MDI) and volumatic spacer to assess reversibility. A cut-off point for significant reversibility of 12% of FEV₁ predicted and 200ml will be taken as supportive of a diagnosis of asthma. Clinic spirometry will be carried out as part of the protocol for induced sputum.

Home spirometry: The subjects will be provided with a portable PiKo-1 spirometer (nSpire Health, Hertford, UK) to carry out daily measurements of FEV₁, FVC and PEF at home. At the baseline visit the subjects will be instructed in the use of the spirometer and will commence measurements to gain familiarity with its use. Measurements will be continued daily for the 6 weeks after inoculation.

9.6 HISTAMINE CHALLENGE (PC₂₀)

Histamine challenge (maximum concentration 16 mg/mL) will be performed according to American Thoracic Society (ATS) guidelines by using the 2 minute tidal breathing method [24]. The provocative concentration of histamine causing a 20% reduction in FEV₁ (PC₂₀) is then calculated.

9.7 EXHALED NITRIC OXIDE (FENO)

Measurement of FeNO levels will be performed using a NIOX VERO device (Aerocrine, Solna, Sweden) with single use patient filters on study visits as per Table 1, and prior to all other assessments. The patient should not eat or drink or participate in any strenuous physical activity for at least one hour prior to testing. The measurement of FeNO will be performed according to American Thoracic Society (ATS) guidelines [25]:

- Patients should be seated comfortably
- Explain test procedure to patient, emphasising that it is a relaxed manoeuvre
- Instruct patient to
 1. Empty their lungs by breathing out thoroughly
 2. Close their lips around the mouthpiece on the patient filter so that no air leakage occurs
 3. Inhale deeply through the patient filter to Total Lung Capacity (TLC)
 4. Exhale slowly through the filter using the display as a guide to the required exhalation pressure and duration

The instrument will analyse the sample and generate a result in parts per billion (PPB) in approximately one minute.

9.8 ELECTROCARDIOGRAM (ECG)

All patients eligible to participate in the study will have a single electrocardiogram (ECG), as part of routine assessment for any medical abnormalities.

9.9 URINE PREGNANCY TEST

All female patients eligible to participate in the study will have a single urine pregnancy test.

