4 PARTICIPANT ENTRY

4.1 PRE-RANDOMISATION EVALUATIONS

Potential subjects for the study will be recruited from hospital outpatient clinics, GP surgeries, spirometry sessions/clinics, other research projects, and advertisements. They will attend the respiratory clinic at St Mary's Hospital, where the outline of the study will be explained to them and a Participant Information Sheet (PIS) provided. They will be given the opportunity to ask questions and be informed that their participation is voluntary. Subjects may decide they wish to have more time to consider taking part in the study, in which case a follow up appointment will be made, or they may continue with the screening process. When a subject has had enough time to consider their participation in this study, and only when they have agreed to take part, they will be asked to read, sign and date a consent form in the presence of the investigator who will also sign the consent form. A copy will be kept in the research file, a copy given to the patient and a copy put into their medical notes.

After signing a consent form, eligible subjects will undergo screening. Screening involves taking a medical history and examination, lung function testing, a histamine challenge, FeNO levels, skin prick testing, blood tests, a urine pregnancy test, and a chest radiograph to assess suitability against the defined inclusion and exclusion criteria. Blood tests include general screening for underlying illness, specifically full blood count, urea and electrolytes, liver function tests, coagulation, and C-reactive protein (CRP), as well as serology for rhinovirus 16 (RV-16). They will be matched to the inclusion/exclusion criteria, which have been maintained from previous studies using the rhinovirus-induced asthma exacerbation model.

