4.3 EXCLUSION CRITERIA

- Presence of clinically significant diseases other than asthma (cardiovascular, renal, hepatic, gastrointestinal, haematological, pulmonary, neurological, genitourinary, autoimmune, endocrine, metabolic, neoplasia etc.), which, in the opinion of the investigator, may either put the patient at risk because of participation in the trial, or diseases which may influence the results of the study or the patient's ability to take part in it
- Smoking history over past 12 months.
- Seasonal allergic rhinitis symptoms at screening or during the 3 week run-in (prior to rhinovirus inoculation).

- Asthma exacerbation or viral illness within the previous 6 weeks or during the 3 week run-in (prior to rhinovirus inoculation).
- Current or concomitant use of oral steroids, anti-leukotrienes or monoclonal antibodies.
- Pregnant or breast-feeding women. Patients should not be enrolled if they plan to become pregnant during the time of study participation (see note regarding contraception below).
- Contact with infants <6 months or immunocompromised persons, elderly and infirm at home or at work.
- Subjects who have known evidence of lack of adherence to medications and/or ability to follow physician's recommendations.

Contraception: To prevent pregnancy, male subjects with female partners of child bearing potential and female subjects must use at least two forms of adequate contraception for the entire duration of study participation. Adequate contraceptive precautions include:

1. Established use of oral, injected or implanted hormonal methods of contraception.
2. Placement of an intrauterine device (IUD) or intrauterine system (IUS).
3. Barrier methods of contraception: condom or occlusive cap (diaphragm or cervical/vault caps) with spermicidal foam/gel/film/cream/suppository.
4. Male sterilisation (with the appropriate post-vasectomy documentation of the absence of sperm in the ejaculate).

Men whose partners are already pregnant must continue to use contraception i.e. a condom during the trial and for three months thereafter. The chosen contraception method(s) must be followed from the first Investigational Medicinal Product (IMP) administration until at least 3 months after receiving the last dose of the IMP.

Sperm donation: Male subjects must not donate sperm throughout the study and for at least 3 months after the final dose of IMP.

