5 RANDOMISATION AND ENROLMENT PROCEDURE

5.1 RANDOMISATION PRACTICALITIES

Subjects who meet the relevant criteria and provide informed consent will be randomised to either OC459 or placebo in a 1:1 ratio. Randomisation will occur at a baseline visit after the screening visit(s), and will be in blocks of four in order to balance the number of patients allocated to each treatment group. An unblinded randomisation list (taking into account the blocking requirements) will be generated by Sealed Envelope Ltd and entered into the study database. This file will be password protected, with unblinding instructions provided by the database development team to the investigators.

At randomisation, the database will be interrogated and each new subject assigned the next sequential randomisation item on the list. The unblinded randomisation list will also be provided to the manufacturer, Atopix Ltd, in order to label IMP/placebo appropriately prior to dispensing to pharmacy. Thus the investigators, pharmacy and subjects will all be blinded.

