7.5 POST-TRIAL TREATMENT

The IMP is unlicensed and therefore will not be made available to participants beyond the end of the study.

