9 ASSESSMENT AND FOLLOW-UP

9.1 SUMMARY OF STUDY ASSESSMENTS AND PROCEDURES

After screening and providing informed consent, eligible participants will undergo baseline investigations and randomisation, followed by a 21 day run-in period on placebo or OC459. Towards the end of this period they will have a baseline bronchoscopy and other investigations. At the end of the run-in period, subjects will have a further set of investigations prior to rhinovirus inoculation the same day. Regular sampling and assessments will take place as indicated whilst treatment administration continues uninterrupted for a further 14 days, for a total of 5 consecutive treatment weeks. Trial medications are then stopped (day 14). Subjects will attend for a final follow-up visit 4 weeks later with convalescence investigations (day 42). Table 1 summarises subject visits and procedures during the study. Details of the individual study procedures are listed below.

Study participants will be seen frequently during the study period, daily if they wish. They have details to contact the Clinical Research Fellow and Clinical Research Nurse, and will be offered daily telephone contact. In this way participants will be assessed regularly by the investigating team and any adverse events detected rapidly. When the study is completed, subjects will return to the care of their GP (they will not be routinely followed-up by the study group).

	Screening visit 1	Screening visit 2	Visit 1 (baseline)	Visit 2	Visit 3	Visit 4	Visit 5	Visit 6	Visit 7	Visit 8	Visit 9	Visit 10	Visit 11
Study day			-21	-9	-8	0	2	3	4	5	7	10	42
Ideal weekday			F	W	T	F	Su	M	T	W	F	M	F
Visit length	30 min	60 min	60 min	45 min	3 hr	60 min	45 min	45 min	45 min	3 hr	60 min	45 min	30 min
Skin prick test	X												
Viral serology	X												X
Asthma Control Questionnaire (ACQ)	X		X	X		X						X	X
Spirometry (in clinic)	X		X	X		X	X	X	X	X	X	X	X
Histamine challenge (PC ₂₀)		X	X	X							X		
Exhaled nitric oxide (FeNO)		X	X	X		X		X		X	X	X	X
Blood tests		X	X		X			X		X		X	X
ECG		X											
Urine pregnancy test		X											
Chest radiograph		X											
IMP or placebo administration			Daily from day -21 → day 14 (then stop)										
Nasosorption			X			X	X	X	X	X	X	X	
Nasal lavage			X			X	X	X	X	X	X	X	
Nasal scrape			X		X			X		X			
Bronchoscopy (bronchosorption, BAL, brushings, biopsies)					X					X			
Sputum induction			X	X					X		X		
Virus inoculation						X							

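### The only scheduled pregnancy test is at Screening visit 2; it is not repeated before randomisation and first dose at Day -21, and no maximum interval is set between the two

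*Protocol*

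**What the plan says.** Protocol 4.3 lists as an exclusion: "Pregnant or breast-feeding women. Patients should not be enrolled if they plan to become pregnant during the time of study participation". SAP 4.3 repeats it. Protocol 4.1 places the pregnancy test among the screening procedures used to judge eligibility, and Protocol 9.9 fixes the number: "All female patients eligible to participate in the study will have a single urine pregnancy test".

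In Table 1 (Protocol 9.1 and SAP 4.9), the row "Urine pregnancy test" carries one mark, under Screening visit 2. Visit 1 (Day -21) and every later visit are blank. The screening visits have no study day. Protocol 5.1 puts randomisation at a baseline visit after screening, and Table 1 starts daily dosing at Day -21.

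On contraception, Protocol 4.3 says "female subjects must use at least two forms of adequate contraception for the entire duration of study participation". Later in the same section it says that the chosen methods must be followed starting with the first dose of study drug and for at least 3 months after the last.

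**The concern.** Pregnancy status can change between screening and dosing. As written, the exclusion is tested once, at an unspecified distance before the first dose, and is not rechecked when it matters. A woman who conceived after Screening visit 2, or too shortly before it for the test to react, could be randomised without any scheduled step that would show it.

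She would then start a drug of which Protocol 7.5 says "The IMP is unlicensed and therefore will not be made available to participants beyond the end of the study". Without disclosure or an unscheduled test, she would go on to two bronchoscopies, with sedation as necessary (Protocol 9.14), and to RV-16 inoculation. The protocol itself takes exposure in pregnancy seriously, since it asks for two contraceptive methods and continues them for 3 months after dosing. What is at stake is the safety of individual subjects, not the trial's inference.

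**Working it through.** The plan gives no figure on this point, so there is nothing to reproduce. The check has two parts.

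**Reading the schedule**

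- Pregnancy tests scheduled: 1 (Screening visit 2). Tests at Day -21: 0. Tests from Day -21 to Day 42: 0.
- Stated maximum interval from test to first dose: none.
- Other tests that could close the gap: none. Neither the screening bloods listed in Protocol 9.3 nor Table 2 there includes hCG.
- From first dose at Day -21, bronchoscopy 1 (Day -8) is 13 days later, inoculation (Day 0) 21 days later and bronchoscopy 2 (Day 5) 26 days later.
- Contraception: Protocol 4.1 says "After signing a consent form, eligible subjects will undergo screening". If study participation begins at consent, the first contraception sentence covers the gap. The second starts the obligation at first dose and so leaves the gap uncovered. The text does not settle which governs.

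**Size**

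Only the 44 enrolled subjects come from the documents. The rest are assumptions: 22 women (range 11 to 33), gap from test to first dose 4 weeks (1 to 8), conception rate 3% per year (1% to 5%), and a urine test that misses conceptions in the most recent 2 weeks.

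*What a Day -21 test would add.* The screening test misses conceptions from 2 weeks before it onwards. A Day -21 test misses those from 2 weeks before Day -21 onwards. The extra window that it covers is therefore as long as the gap itself, whatever the lag, provided that the lag is the same for both tests.

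Detected = women x gap/52 x annual rate

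- Central: 22 x 4/52 x 0.03 = 0.051
- Low: 11 x 1/52 x 0.01 = 0.002
- High: 33 x 8/52 x 0.05 = 0.254

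The central value splits equally. Conceptions in the 2 weeks before screening, which the first test was too early to see, give 22 x 2/52 x 0.03 = 0.025. Conceptions in the first 2 weeks after screening give another 0.025.

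The central value is about one detection in 1/0.051 = 20 trials of this size, or roughly 20 x 22 = 440 added tests per detection.

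*What it would not address.*

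- Conceptions in the 2 weeks before Day -21: 22 x 2/52 x 0.03 = 0.025
- Conceptions during the 5 dosing weeks: 22 x 5/52 x 0.03 = 0.063

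Pregnancies present at first dose but not shown by the screening test therefore total about 0.051 + 0.025 = 0.076. The added test would find about two thirds of them (0.051/0.076).

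**The case against.** The other side has a fair case. No requirement in the documents is broken: the exclusion, the single test and both schedules agree with one another, and nothing in them says that eligibility tests must be repeated at dosing. Women planning a pregnancy are not enrolled, and two contraceptive methods are required. Frequent visits, the offer of daily telephone contact, separate consent for each bronchoscopy and the investigator's power to withdraw a subject all give openings to disclose a missed period. The expected yield is tiny and rests on assumed inputs. The conception rate is the weakest of them: two concurrent methods could make 3% too high, while a gap without mandatory contraception could make it too low.

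Most of this stands as an argument about weight. None of it supplies a check of pregnancy status before first dose.

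Three stronger readings are tempting, and the documents do not support them.

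- A reader might infer that the gap is certainly without contraception. Section 4.3 is inconsistent, so this cannot be asserted either way.
- A reader might take the exclusions for seasonal rhinitis symptoms and for exacerbation or viral illness, which run through the run-in, as proof that pregnancy was singled out for neglect. Those exclusions extend after Day -21 and plausibly protect the post-inoculation symptom score. They are not a Day -21 recheck that pregnancy lacks.
- A reader might assume that any affected woman would be sedated twice. Protocol 9.14 makes sedation conditional on need.

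**Conclusion.** The gap is real. One urine test at Screening visit 2 is the only scheduled verification of the pregnancy exclusion; it is not repeated before randomisation and first dose, and the interval is unlimited. Contraception lowers the risk but does not verify the exclusion, and its start is stated inconsistently.

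The probability is low: about 0.05 detectable pregnancies per trial (0.002 to 0.25), conditional on the assumed number of women, gap and conception rate, and on applying the same rate just before screening as after it. The case for acting rests on a potentially serious consequence for one person set against a very small cost, not on the expected count.

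A reader might infer that a Day -21 test would close off exposure in pregnancy. It would not: about 0.025 very recent conceptions and about 0.06 during dosing fall outside it, together more than it detects. Nor does the point bear on the primary analysis, power or error rates. It is a cheap improvement to safety.

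**What to change.** Add a mark at Visit 1 (Day -21) in the pregnancy-test row of Protocol Table 1 and mirror it in SAP Table 1. Amend Protocol 9.9 so that every female subject is tested at Screening visit 2 and again at Visit 1, with a negative Visit 1 result required before randomisation and first dose. The same amendment could usefully align the two statements in Protocol 4.3 on when contraception starts.

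The cost is one dipstick per woman (22 if half the subjects are women, range 11 to 33) at an existing 60-minute visit that already has nine marked procedures, plus a short amendment. No visit is added. A positive result occasionally loses a subject, but before randomisation, so no randomised subject has to be replaced. The contraception rule must stay, because a negative test does not exclude a very recent or later conception.
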